#### **7.4.2. Laboratory Assessments**

All protocol required laboratory assessments, as defined in the Time and Events Schedule (see Section 7.1), must be performed by the central laboratory. Laboratory assessments must be conducted in accordance with the Central Laboratory Manual and Protocol Time and Events Schedule. Laboratory requisition forms must be completed and samples must be clearly labeled with the participant number, protocol number, site/centre number, and visit date. Details for the preparation and shipment of samples will be provided by the central laboratory. Reference ranges for all safety parameters will be provided to the site by the central laboratory.

If additional non-protocol specified laboratory assessments are performed at the institution's local laboratory and result in a change in subject management or are considered clinically significant by the investigator (e.g., SAE or AE or dose modification) the results must be recorded in the eCRF. Local laboratory services may be used to verify pending laboratory parameters only after consultation and agreement with the study team.

Refer to the lab manual for appropriate processing and handling of samples to avoid duplicate and/or additional blood draws.

Labs will be automatically graded by the central lab according to the DAIDS toxicity scales (See Section 12.2 "Division of AIDS Table for Grading the Severity of Adult and Pediatric Adverse Events").

For fasting laboratory assessments, an overnight fast is preferred; however, a minimum of a 6 hour fast is acceptable.

Table 6 includes lab parameters to be assessed as per the Time and Events Schedule (see Section 7.1):

**Table 6 Safety Laboratory Assessments**

Hematology			
Platelet count	Automated WBC differential:		
RBC count	Neutrophils		
WBC count (absolute)	Lymphocytes		
Hemoglobin	Monocytes		
Hematocrit	Eosinophils		
MCV	Basophils		
Clinical Chemistry			
BUN	Potassium	AST	Total bilirubin a
Creatinine	Chloride	ALT	Albumin
Glucose c	Total CO 2	Alkaline phosphatase	Creatine phosphokinase
Sodium	Lipase	Phosphate	Creatinine clearance b
Fasting Lipid Paneld			
Total cholesterol			
HDL cholesterol			
LDL cholesterol			
Triglycerides			
Other Tests			
Plasma HIV-1 RNA e			
CD4+ and CD8+ cell counts [CD4/CD8 ratio] f			
Peripheral Blood Mononuclear Cells (PBMCs): Day 1, Week 96, Withdrawal only			
Hepatitis B (HBsAg), anti-HBc, anti-HBsAg, and hepatitis C antibody (Screening) g			
Rapid Plasma Reagin (RPR) (Screening and Baseline)			
HLA-B*5701 (Screening only)			
Prothrombin Time (PT)/International Normalized Ratio (INR)/ Partial Thromboplastin Time (PTT)			
Pregnancy test for women of childbearing potential h			
Urinalysis, urine albumin/creatinine ratio, and urine protein/creatinine ratio, urine phosphate			
Genetics Sample			
Renal biomarkers including Cystatin-C (blood), Retinol Binding Protein (RBP, blood/urine) i			
Bone biomarkers including: Bone-specific alkaline phosphatase, procollagen type 1 N-propeptide, type 1 collagen cross-linked C-telopeptide, osteocalcin, 25 hydroxy-Vitamin D i			
Follicle stimulating hormone (FSH) and estradiol (only for instances when postmenopausal status is questionable)			

MCV = mean corpuscular volume, RBC = red blood cells, WBC = white blood cells, BUN = Blood urea nitrogen, AST=aspartate aminotransferase, ALT = alanine aminotransferase, CO2 = carbon dioxide, HDL = high density lipoprotein, LDL = low density lipoprotein, HBsAg= hepatitis B virus surface antigen, PT/INR = prothrombin time/international normalized ratio.

- Direct bilirubin will be reflexively performed for all total bilirubin values  $>1.5 \times$  ULN.
- Glomerular filtration rate (GFR) will be estimated by the central laboratory using the Chronic Kidney Disease Epidemiology Collaboration (CKD-EPI) [Levey, 2009].
- For fasting glucose assessments, an overnight fast is preferred; however, a minimum of a 6-hour fast is acceptable for participants with afternoon appointments.
- For fasting lipids assessments, an overnight fast is preferred; however, a minimum of a 6-hour fast is acceptable for participants with afternoon appointments.
- For participants meeting virologic withdrawal criteria, plasma samples will be analyzed in attempt to obtain genotype/phenotype data.
- CD8+ cells will only be reported at Baseline, Day 1, Weeks 4b, 24, 48, and 96.
- HBV DNA will only be performed for participants with a positive anti-HBc and negative HBsAg and negative anti-

- HBs (past and/or current evidence).
- h) Urine pregnancy test/ serum pregnancy test will be performed according to the Time and Events Table (Section 7.1).
- i) Since the intention is to utilize these biomarker data for research purposes, the sponsor will not be reporting the results of these assessments to the investigator, except for 25 hydroxy-vitamin D.

### **7.4.3. Adverse Events (AE) and Serious Adverse Events (SAEs)**

The investigator and their designees are responsible for detecting, documenting and reporting events that meet the definition of an AE or SAE.

#### **7.4.3.1. Time period and Frequency for collecting AE and SAE information**

- Any SAEs assessed as related to study participation (e.g., protocol-mandated procedures, invasive tests, or change in existing therapy) or related to a GSK product will be recorded from the time a participant consents to participate in the study up to and including any follow-up contact.
- AEs will be collected from the start of Study Treatment until the follow-up contact (see Section 7.4.3.1), at the timepoints specified in the Time and Events Table (Section 7.1).
- Medical occurrences that begin prior to the start of study treatment but after obtaining informed consent may be recorded on the Medical History/Current Medical Conditions section of the eCRF.
- The method of recording, evaluating and assessing causality of AEs and SAEs plus procedures for completing and transmitting SAE reports to GSK are provided in Section 12.6, Appendix 6
- Investigators are not obligated to actively seek AEs or SAEs in former study participants. However, if the investigator learns of any SAE, including a death, at any time after a participant has been discharged from the study, and he/she considers the event reasonably related to the study treatment or study participation, the investigator must promptly notify GSK.
- During the Extension Phase, AEs leading to Withdrawal and all SAEs will be recorded.

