
To evaluate the antiviral and immunologic effects, safety, tolerability, and viral resistance of CAB LA + RPV LA for participants during the Extension Phase
 
 
● For participants randomized to CAB LA+ RPV LA at Day 1
 
● For participants electing to transition to CAB LA + RPV LA in the Extension Phase
 
	
 
● Proportion of participants with plasma HIV-1 RNA <50 c/mL over time including week 96 (Observed Case).
 
● Proportion of participants with confirmed virologic failure (two consecutive plasma HIV-1 RNA levels <math>\geq 200</math> c/mL after prior suppression to <200 c/mL) through Week 96
 
● Absolute values and change from Baseline in plasma HIV-1 RNA over time including Week 96
 
● Absolute values and changes from Baseline in CD4+ cell counts over time including Week 96
 
● Incidence of disease progression (HIV-associated conditions, acquired immunodeficiency syndrome [AIDS] and death)
 
● Incidence and severity of AEs and laboratory abnormalities over time including Week 96
 
● Proportion of participants who discontinue treatment due to AEs over time including Week 96
 
● Absolute values and changes in laboratory
 

Objectives	Endpoints
	
parameters over time including Week 96
 
 
● Incidence of treatment emergent genotypic and phenotypic resistance to CAB, RPV, and other on study ART at Week 96
 

To assess the acceptance of pain and injection site reactions following injections	
 
● Change from Week 5 in Dimension scores (“Bother of ISRs”, “Leg movement”, “Sleep”, and “Injection Acceptance”) and individual item scores assessing pain during injection, anxiety before and after injection, willingness to be injected in the future and overall satisfaction with mode of administration over time using the Perception of iNjection questionnaire (PIN)
 
● Proportion of participants considering pain and local reactions following injection to be extremely or very acceptable based on the acceptability score over time using the Perception of iNjection questionnaire (PIN)
 

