- Pregnancy testing. A negative urine pregnancy test is required prior to initiation of IP, any dose of CAB LA or RPV LA or as required by the Medical Monitor following a treatment interruption(s). If serum testing is required locally, the results should be available prior to the visit where urine testing is indicated per the Time and Events Schedule (Section 7.1).
- Evaluation and documentation of all concomitant medications and blood products.
- Injection Site Reactions (ISRs) will be assessed clinically during the Maintenance and Extension Phases for the following:  
Pain, tenderness, pruritis, warmth, bruising, discoloration, infections, rash, erythema, swelling, induration, and nodules (granulomas or cysts).
- A clinical assessment (using Division of Acquired Immunodeficiency Syndrome [DAIDS] grading scale) should be performed both before and after an injection to identify resolving and new ISRs. All injection site reactions are considered adverse events. The clinical assessment and interpretation of any ISR, will be documented in the ISR AE eCRF.
- Columbia Suicide Severity Rating Scale (eC-SSRS) will be assessed as per the Time and Events Schedule (see Section 7.1 and Suicidal Risk Monitoring Section 7.4.5).

Any appropriately qualified site personnel (e.g., Investigator, sub-Investigator, or study coordinator/nurse) can perform assessments.

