#### **9.4.9. Other Analyses**

The proportion of participants with virologic failure ( FDA Snapshot algorithm) and HIV-1 RNA <50 c/mL (FDA snapshot algorithm), respectively, over time through Week 48 will be analysed by important demographic and baseline characteristic subgroups factors (e.g. age, gender, BMI, race, HIV-1 subtype, and Baseline CD4+ cell counts). Changes from baseline in CD4+ lymphocyte count at Week 48 will also be summarized by subgroups. Additional details on subgroup analyses will be provide in the RAP.

Longer term antiviral and immunological effect, safety and tolerability of CAB LA + RPV LA will be assessed through Week 96 for the CAB LA + RPV LA arm (48 weeks of comparative data and 48 weeks of extension data). Antiviral and immunological effect, safety and tolerability of CAB LA + RPV LA will also be evaluated for participants switching to CAB LA + RPV LA in the Extension Phase.

Further details of exploratory analyses will be presented in the RAP.

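### Section 7.4.3.1 gives two adverse event recording rules that disagree; if the narrower one governs, the Week 96 adverse event endpoint will be incomplete

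*Protocol*

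**What the plan says.** Two bullets of Protocol Section 7.4.3.1 bear on this. The second reads "AEs will be collected from the start of Study Treatment until the follow-up contact (see Section 7.4.3.1), at the timepoints specified". The schedule it points to is the Time and Events Table, and the bullet draws no line between phases. The last reads "During the Extension Phase, AEs leading to Withdrawal and all SAEs will be recorded".

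Section 3 sets an Extension Phase objective for two groups: participants randomized to CAB LA + RPV LA at Day 1, and a second group described as "For participants electing to transition to CAB LA + RPV LA in the Extension Phase". Its secondary endpoints include "Incidence and severity of AEs and laboratory abnormalities over time including Week 96" and, as a separate item, "Proportion of participants who discontinue treatment due to AEs over time including Week 96". Section 9.4.2 plans summaries of all AEs by incidence and severity, and Section 9.4.9 says that "safety and tolerability of CAB LA + RPV LA will also be evaluated for participants switching" in the Extension Phase.

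Section 7.4.1 has injection site reactions (ISRs) assessed in both the Maintenance and Extension Phases, states that "All injection site reactions are considered adverse events", and sends them to their own eCRF form.

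**The concern.** An endpoint on AE incidence and severity needs every AE, not just the serious ones and those that end treatment. If sites follow the last bullet, ordinary non-serious events stop being entered at Week 52. No later analysis plan can recover events that were never entered.

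Three things are at stake:
- The Week 96 endpoint would mix full capture before Week 52 with partial capture after it, so AE incidence would appear to fall because of the recording rule.
- Control participants first take CAB + RPV at Week 52, so their whole exposure falls in the period of reduced capture.
- Sites that follow the second bullet and sites that follow the last would record differently, and the two could not be separated in the data.

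**Working it through.** The check is mainly a comparison of texts.

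1. **Does the last bullet restrict?** The second bullet already covers SAEs and AEs leading to withdrawal in every phase. If it governs throughout, the last bullet is redundant. The last bullet has a function only as a reduction, and that is its natural reading, although it does not use the word only.

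2. **Can the Time and Events Table settle it?** The second bullet defers to that table. Its AE row is not legible in the text available here, so it could not be used to decide between the rules.

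3. **What does Section 3 need?** Discontinuation due to AEs is listed separately from AE incidence and severity. The latter must therefore cover more than withdrawal events. Under the narrow rule the discontinuation endpoint remains fully reportable, while the incidence and severity endpoint does not.

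4. **What is captured under either reading?**
   - SAEs and AEs leading to withdrawal (7.4.3.1).
   - ISRs, on the ISR AE eCRF with no limit by seriousness (7.4.1).
   - Laboratory abnormalities, graded by the central laboratory (7.4.2).
   - Seizures and liver events (7.4.3.4), listed cardiovascular events (7.4.3.7), rash (7.4.4.13) and possible suicidality events (7.4.5), each under its own reporting rule.

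   What remains at risk is the general body of non-serious AEs that do not lead to withdrawal.

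5. **Who is affected?** Both Extension groups. Switching control participants start oral CAB + RPV at Week 52 and injections at Week 56b (4.2.3.2), so none of their exposure precedes the Extension Phase. Their number is at most 285, the size of the control arm (4.5).

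6. **How large could the gap be?** The documents give no rate of general AEs, so only bounds are possible. Consider the AEs outside the separately captured types in step 4. Let p be the share of these that are serious or lead to withdrawal. Assume a constant rate r and follow-up to Week 96.
   - Weeks under the narrow rule: 96 − 52 = 44, or 44/96 = 46% of the period.
   - Recorded rate after Week 52: p × r, against r before. Any p below 1 gives an apparent fall with no change in true risk.
   - CAB LA + RPV LA arm, share recorded over 96 weeks: (52 + 44p)/96. This runs from 52/96 = 54% at p = 0 to 100% at p = 1.
   - Switchers, share recorded: p, because all their exposure lies after Week 52.

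**The case against.** The strongest reply is that the contradiction is milder than it looks. The last bullet does not say only, and the second bullet, "AEs will be collected from the start of Study Treatment until the follow-up contact", can be read as governing throughout. On that reading all AEs are collected and the endpoint is reportable. The affected data are also uncontrolled secondary data: the primary endpoint, the randomized comparison and comparative safety to Week 48 all precede the Extension Phase.

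Several stronger readings are tempting, and the documents do not support them:
- **The endpoint cannot be reported at all.** Much of the safety data survives either rule (step 4 of the working). The accurate word is incomplete, and then only if the last bullet governs.
- **Nearly all ISRs would go unrecorded.** Section 7.4.1 names the Extension Phase and has any ISR documented on its own form. ISRs are better seen as a further conflict: all of them count as AEs, yet the last bullet would exclude the non-serious ones that do not end treatment.
- **Events of special interest would be lost.** Seizures, the special-interest event named in Section 4.8.1.1, have a separate 24-hour reporting rule with no Extension Phase exemption.
- **The gap affects 285 newly exposed participants.** That is a ceiling. Some will be ineligible or decline. Section 4.3 expects most participants to move to ATLAS-2M, and Section 4.3.1 lets control participants go there directly at Week 52.

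These points limit the size of the problem. They do not tell a site which of the two bullets to follow.

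**Conclusion.** Section 7.4.3.1 contradicts itself, and its last bullet does not support the Week 96 AE incidence and severity endpoint in Section 3 or the evaluation of switchers in Section 9.4.9. The consequence is conditional. If the last bullet governs, general non-serious AEs not leading to withdrawal are missed from Week 52: 44 of the 96 weeks for the CAB LA + RPV LA arm, and all CAB + RPV exposure for the switchers, who number at most 285 and probably well under that. If the second bullet governs, nothing is lost, but the last bullet is then misleading and should go.

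The conclusion assumes that the Time and Events Table does not resolve the conflict; its AE row should be checked. It does not touch the Week 48 primary analysis. It is still an error in a data collection rule rather than a detail for the analysis plan, because the loss cannot be undone.

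**What to change.** Reconcile the two bullets of Section 7.4.3.1 with Section 3. Either delete the last bullet or make it apply only after Week 96. State that all AEs, with grade, are recorded through Week 96 in both Extension groups, and confirm that ISRs continue to be entered as Section 7.4.1 requires. Check that the AE row of the Time and Events Table agrees.

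Make the change before participants enter the Extension Phase. If some already have, issue the clarification at once and establish which rule each site has been following, so that any gap can be described.

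The cost is a protocol clarification and additional AE data entry at visits already held every 4 weeks. No new visits or procedures are needed.

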#### **7.4.3.2. Method of Detecting AEs and SAEs**

Care will be taken not to introduce bias when detecting AEs and/or SAEs. Open-ended and non-leading verbal questioning of the participant is the preferred method to inquire about AE occurrence. Appropriate questions include:

- “How are you feeling?”
- “Have you had any (other) medical problems since your last visit/contact?”
- “Have you taken any new medicines, other than those provided in this study, since your last visit/contact?”

#### **7.4.3.3. Follow-up of AEs and SAEs**

After the initial AE/SAE report, the investigator is required to proactively follow each participant at subsequent visits/contacts. All SAEs, and non-serious AEs of special interest (as defined in Section 7.4.4) will be followed until resolution, until the condition stabilizes, until the event is otherwise explained, or until the participant is lost to follow-up (as defined in Section 5.5). Further information on follow-up procedures is given in Section 12.6, Appendix 6).

#### **7.4.3.4. Prompt Reporting of Serious Adverse Events and Other Events**

SAEs, pregnancies, and liver function abnormalities meeting pre-defined criteria will be reported promptly by the investigator to the medical monitor as described in Table 7 once the investigator determines that the event meets the protocol definition for that event. Any seizure or suspected seizure should be reported in an expedited manner, as noted in Table 7.

Criteria for liver chemistry stopping and follow-up criteria are in Section 5.5.1.

**Table 7 Reporting of Serious Adverse Events and Other Events**

Type of Event	Initial Reports		Follow-up Information on a Previous Report	
	Time Frame	Documents	Time Frame	Documents
All SAEs	24 hours	“SAE” data collection tool	24 hours	Updated “SAE” data collection tool
Cardiovascular or death event	Initial and follow-up reports to be completed when the cardiovascular event or death is reported a	“CV events” and/or “death” data collection tool(s) if applicable	Initial and follow-up reports to be completed when the cardiovascular event or death is reported a	Updated “CV events” and/or “death” data collection tool(s) if applicable
Pregnancy	24 hours	“Pregnancy Notification Form”	Within 24 hours of investigator awareness of pregnancy outcome	“Pregnancy Follow-up Form” and SAE if required
Seizure or suspected seizure	24 hours	eCRF	24 hours	eCRF
Suspected ABC HSR in participants randomized to the current ART arm or receiving Oral SOC during the Long-Term Follow-Up Phase b	1 week	ABC HSR eCRF	1 week	Updated ABC HSR eCRF
ALT $\geq$ 3 $\times$ ULN and bilirubin $\geq$ 2 $\times$ ULN (>35% direct) (or ALT $\geq$ 3 $\times$ ULN)	24 hours c	“SAE” data collection tool. “Liver Event eCRF” and “Liver Imaging” and/or “Liver Biopsy” eCRFs, if applicable d	24 hours	Updated “SAE” data collection tool/“Liver Event” documents d

Type of Event	Initial Reports		Follow-up Information on a Previous Report	
	Time Frame	Documents	Time Frame	Documents
ALT $\geq$ 5 $\times$ ULN that persists $\geq$ 2 weeks	24 hours c	Liver Event eCRF d	24 hours	Updated Liver Event eCRF d
ALT $\geq$ 8 $\times$ ULN	24 hours c	Liver Event eCRF d	24 hours	Updated Liver Event eCRF d
ALT $\geq$ 3 $\times$ ULN (if baseline ALT is <ULN) or ALT $\geq$ 3 fold increase from baseline value with appearance or worsening of symptoms of hepatitis or hypersensitivity	24 hours c	Liver Event eCRF d	24 hours	Updated Liver Event eCRF d

- Additional details and time frames for reporting supplementary information for cardiovascular and death events are provided in Section 7.4.3.7 and Section 7.4.3.8, respectively.
- ABC HSR eCRF only required if event meets one of the ICH E2A definitions of seriousness.
- GSK must be contacted at onset of liver chemistry elevations to discuss participant safety.
- Liver event documents (i.e., "Liver Event eCRF" and updates, "Liver Imaging eCRF" and/or "Liver Biopsy eCRF", as applicable) should be completed as soon as possible.

The method of recording, evaluating, and follow-up of AEs and SAEs plus procedures for completing and transmitting SAE reports to the medical monitor are provided in the SPM. Procedures for post study AEs/SAEs are provided in the SPM. Primary and secondary Medical Monitor/SAE contact information is provided on the Medical Monitor/Sponsor Information Page of the current protocol.

#### 7.4.3.5. Disease-Related Events and/or Disease-Related Outcomes Not Qualifying as SAEs

Disease related events (DREs) or outcomes listed in the CDC Classification System for HIV-1 Infections ([Appendix 4](#)) can be serious/life threatening and will be recorded on the HIV-Associated Conditions eCRF page if they occur. However, these individual events or outcomes, as well as any sign, symptom, diagnosis, illness, and/or clinical laboratory abnormality that can be linked to any of these events or outcomes are not reported to GSK as AEs and SAEs even though such event or outcome may meet the definition of an AE or SAE. However, if either of the following conditions applies, then the event must be recorded and reported as an SAE (instead of a DRE):

- The investigator determines that the event or outcome qualifies as an SAE under part 'other situations' of the SAE definition (see Section 12.6.2), or
- The event is, in the investigator's opinion, of greater intensity, frequency, or duration than expected for the individual participant, or
- The investigator considers that there is a reasonable possibility that the event was related to treatment with the investigational product, or

- Death occurring for any reason during a study, including death due to a disease-related event, will always be reported promptly.
- Lymphomas and invasive cervical carcinomas are excluded from this exemption; they must be reported as SAEs even if they are considered to be HIV-related.

**If any of the above conditions is met then record the DRE on the SAE page rather than the HIV Associated Conditions eCRF page and report promptly (i.e., expedited reporting, see Section 7.4.3.4) to GSK.**

